### 3.2.4 Exploratory Endpoints

Exploratory imaging outcome measures are as follows:

- Change in Macular Volume (MV) from baseline to Week 24 for 1, 3, and 6 mm regions.
  - MV for the 1 mm region is the central 1 subfield, for the 3 mm region is the middle 5 subfields and for the 6 mm region is all 9 subfields as provided by the imaging center
- Change in area of retinal non-perfusion from baseline to Week 24 seen on widefield Fluorescein Angiography (FA).
- Proportion of participants with intact foveal avascular zone (FAZ) seen on widefield FA at Week 24.
- Optical coherence tomography angiography (OCTA) endpoints within the 6mm area:
  - Change from baseline to Week 24 in FAZ area
  - Change from baseline to Week 24 in non-perfusion area
  - Change from baseline to Week 24 in vessel caliber
  - Change from baseline in Ischemic Index at Week 24 defined as total area of non-perfusion divided by total area of retina visualized (28.3 mm^2)

- Proportion of participants with new neovascularization at Week 24
- Proportion of participants with new IRMA at Week 24
- Change in vessel density from baseline to Week 24 in the superficial and deep layers

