
Designation of Study Eye:
 
Only one eye will be designated as the study eye in every participant. For participants who meet eligibility criteria in both eyes during the screening phase, the eye with the higher reading center confirmed DRSS should be selected. If both eyes have the same score, the eye with the clearest lens and ocular media will be selected. If there is no objective basis for selecting the study eye, factors such as ocular dominance (better focus ability), other ocular pathology, and participant preference should be considered in making the selection. The final selection will be done by the Investigator in discussion with the participant at baseline and must not be changed during the course of the study.
 
The non-study eye is eligible for treatment according to the standard of care treatments through the duration of the study.
	

Study procedures/assessments:
 
Assessments will be performed monthly during each clinic visit unless indicated otherwise in the Schedule of Activities (SoA), and include the following:
 
 • Adverse event recording • Review of concomitant medications • Vital signs • Physical examination (Screening Visit only) • Laboratory testing (hematology, blood chemistry, urinalysis, and HbA1c) • Pregnancy testing (as applicable) • BCVA (ETDRS) • Slit-lamp bio-microscopy • Ocular surface health [fluorescein stain of the cornea] • IOP • Indirect ophthalmoscopy/dilated fundus examination • Spectral domain OCT (SD-OCT) (central subfield thickness, macular volume, foveal contour) at every visit 	

- 7-field or 4-wide field color fundus photography at every visit [optional wide-field if available]
- DRSS scoring, based on 7-field or 4-wide field photos by the PI at baseline to confirm eligibility
- Fluorescein angiography (FA) (wide field if available) at baseline and end of study
- OCTA if available (for exploratory endpoints) at baseline and end of study
- Rescue therapy initiation, per alignment between Investigator and Medical Monitor
- HbA1c at screening and end of treatment
- Gonioscopy

Visit Timeline:

Screening – Visit 1; Baseline (BL) – Visit 2; Week 4 – Visit 3; Week 8 – Visit 4; Week 12 – Visit 5; Week 16 – Visit 6; Week 20 – Visit 7; Week 24 – Visit 8

Rescue Criteria:

Participants meeting any of the following criteria would qualify for rescue with anti-VEGF therapy and/or PRP laser after consultation with the Medical Monitor:

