| 
To evaluate the change in DME in participants treated with OTT166
   | 
 
• Change in Macular Volume (MV) from baseline to Week 24 for 1-, 3-, and 6-mm regions
 
   |

|  |  |
|--|--|
| 
To assess the effects of treatment on anatomic markers other than DRSS and on retinal non-perfusion
 | 
 
• Change in area of retinal non-perfusion from baseline to Week 24 seen on widefield fluorescein angiography (FA)
 
• Proportion of participants with intact foveal avascular zone (FAZ) seen on widefield FA at Week 24
 
• Optical coherence tomography angiography (OCTA) endpoints within the 6 mm area:             
 
- Change from baseline to Week 24 in FAZ area
 
- Change from baseline to Week 24 in non-perfusion area
 
- Change from baseline to Week 24 in vessel caliber
 
- Ischemic Index at Week 24 compared to baseline
 
- Proportion of participants with new neovascularization at Week 24
 
- Proportion of participants with new intraretinal microvascular abnormality (IRMA) at Week 24
 
- Change in vessel density from baseline to Week 24 in the superficial and deep layers
 
 
 
 |
|--|--|

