#### 4.10.2 Primary Efficacy Analysis

The primary efficacy outcome measure of the study will be the proportion of participants who have improved by  $\geq 2$  steps from BL DRSS at Week 24. DRSS score levels will be recoded into 12 steps, provided by WRC.

Comparison of the primary endpoint will be made between each dose group and the combined vehicle control group using Mantel-Haenszel (MH) test of the difference in two proportions stratified by the randomization stratification factor (BL DRSS score 47 or 53 or 61B). The estimated MH risk difference will be summarized along with the two-sided 90% CI using MH stratum weights and the Sato variance estimator.

The primary efficacy analysis will be performed on the ITT Analysis Set, while the PPS will be used as a supplementary analysis. ICEs and missing data will be handled as described in [Section 4.10.1.2](#).

In order to assess the robustness of the study conclusions to the choice of imputation method, the following sensitivity analyses will be performed on the ITT Analysis Set and PPS for the primary endpoint:

- An observed case analysis where only observed responses will be used for analysis.  
Observed data after initiation of rescue medication will be set to missing.
- A LOCF analysis where missing post-baseline responses will be imputed using the LOCF procedure.  
Measurements after rescue will be imputed using the last observation prior to rescue treatment; a non-response will be imputed if no post-baseline measurements are available.

A supplementary analysis will be performed on the ITT Analysis Set and PPS for the primary endpoint to assess the time to improvement of  $\geq 2$  steps improvement from BL in DRSS score. Analyses will be based on observed data, where participants who receive rescue medication will be censored at the start of rescue medication (unless improvement of  $\geq 2$  steps improvement from BL in DRSS score is achieved prior to starting rescue medication). This analysis will be presented based on the Kaplan-Meier method, along with a 90% confidence interval. A stratified log-rank test adjusting for the randomization stratification factor will be performed, to compare the combined vehicle control with each treatment group. Additionally, a stratified Cox proportional hazards model adjusting for the randomization stratification factor will be employed to estimate the hazards ratio between the combined vehicle control and each treatment group.

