#### 4.10.4 Exploratory Analysis

Exploratory imaging outcome measures are described in [Section 3.2.4](#).

- All exploratory endpoint analyses will be performed on the Intention-to-Treat Analysis Set and will be based on observed data, where observed data after the initiation of rescue medication will be set to missing unless specified otherwise. The following exploratory endpoint analyses will be repeated on the PPS:
  - Change in MV from baseline to Week 24 for 1, 3, and 6 mm regions.
  - Change in area of retinal non-perfusion from baseline to Week 24 seen on widefield FA.
  - Proportion of participants with intact FAZ seen on widefield FA at Week 24.

The exploratory endpoints involving proportions of participants will be analyzed using the same approach (MH test) as described for the primary efficacy analysis if not specified otherwise.

The time to event exploratory endpoints will be estimated based on the Kaplan-Meier method, along with a 90% confidence interval. A stratified log-rank test adjusting for the randomization stratification factor will be performed, to compare the combined vehicle control with each treatment group. Additionally, a stratified Cox proportional hazards model adjusting for the randomization stratification factor will be employed to estimate the hazards ratio between the combined vehicle control and each treatment group.

Continuous exploratory endpoints involving change from BL will be analyzed using an ANCOVA model with BL measurement of the variable as a covariate and treatment group and the randomization stratification factor as fixed factors. The pair-wise comparisons of each OTT166 dose group versus combined vehicle control will be done in the ANCOVA model. Two-sided 90% confidence intervals for the difference of each OTT166 dose group minus combined vehicle control will be calculated.

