# Parexel International

OcuTerra Therapeutics, Inc.  
OTT166-201

Statistical Analysis Plan

|   |       |       |       |       |       |       |       |       |
|---|-------|-------|-------|-------|-------|-------|-------|-------|
| 4-wide or 7-field color fundus photography (mandatory) e | OU    | OU    | SE    | SE    | OU    | SE    | SE    | OU    |
| SD-OCT (widefield if available)                                     | OU    | OU    | SE    | SE    | OU    | SE    | SE    | OU    |
| OCTA (if available)   | OU    |       |       |       |       |       |       | OU    |
| Wide field Fluorescein Angiography m                     | OU    |       |       |       |       |       |       | OU    |
| Gonioscopy  | OU    |       |       |       |       |       |       | OU    |
| Non-Ocular Assessments:                                      |       |       |       |       |       |       |       |       |
| Physical examination f                                   | X     |       |       |       |       |       |       |       |
| Vital signs g  | X     | X     | X     | X     | X     | X     | X     | X     |
| Adverse events h   | X     | X     | X     | X     | X     | X     | X     | X     |
| IP adherence review n                                    |       |       | X     | X     | X     | X     | X     | X     |
| Laboratory Testing:i                              |       |       |       |       |       |       |       |       |
| Hematology, blood chemistry, urinalysis, and HbA1c j,l   | X     |       |       |       |       |       |       | X     |
| Pregnancy test, women of childbearing potential k        | serum | urine | urine | urine | urine | urine | urine | urine |

Abbreviations: BCVA: best corrected visual acuity; BL: baseline; ETDRS: Early Treatment Diabetic Retinopathy Study; HbA1c: glycosylated hemoglobin; OCTA: optical coherence tomography – angiography; OU: both eyes; SD-OCT: spectral-domain optical coherence tomography; SE: study eye;

a Participants who are withdrawn from the study before Week 24/Visit 8 will be asked to return to the clinic to complete the Visit 8 assessments.

b Participants will continue to receive study treatment based on exam findings, AE review, and verification that rescue criteria are not met.

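### The intact-FAZ endpoint leaves baseline FAZ status unused, and the Ischemic Index with its fixed 28.3 mm² denominator repeats the OCTA non-perfusion-area test

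*SAP*

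**What the plan says.** **FAZ endpoint.** SAP 3.2.4 lists "Proportion of participants with intact foveal avascular zone (FAZ) seen on widefield FA at Week 24", and Protocol 2.20.2 has the same endpoint. Neither document conditions it on status at entry or says how intact is graded. On the test, SAP 4.10.4 states: "The exploratory endpoints involving proportions of participants will be analyzed using the same approach (MH test) as described for the primary efficacy analysis". SAP 4.10.2 describes that primary test as "stratified by the randomization stratification factor (BL DRSS score 47 or 53 or 61B"), so DRSS is the only stratifier.

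**Baseline FA.** The schedule in SAP 6.1 (Table 1 of the protocol) has "Wide field Fluorescein Angiography" in both eyes at Visit 1 and Visit 8. The protocol synopsis lists "Fluorescein angiography (FA) (wide field if available) at baseline and end of study". Under Protocol 2.16.4 the screening images go to the central reading center.

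**Ischemic Index.** SAP 3.2.4 specifies "Change from baseline in Ischemic Index at Week 24 defined as total area of non-perfusion divided by total area of retina visualized", and gives that retinal area as 28.3 mm². The objectives table in SAP Section 2 words it as "Ischemic Index at Week 24 compared to baseline". The same OCTA list, confined to the 6 mm area, has change in non-perfusion area as an endpoint of its own. Under SAP 4.10.4, continuous exploratory changes go into an ANCOVA with the variable's own baseline as covariate and treatment and DRSS stratum as factors.

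**The concern.** Every other FA or OCTA endpoint in SAP 3.2.4 is a change or a new finding. The FAZ endpoint is the exception, and no reason is given. An eye whose FAZ was already disrupted at entry and stayed so counts against its arm exactly as an eye that lost its FAZ on study does. Baseline status is likely to be a strong predictor of Week 24 status, and leaving it out gives up precision that costs nothing to recover.

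The Index raises a different question. The definition reads as a ratio of two measured quantities, but a constant stands in the denominator. If the ratio is only a change of units, the study report will hold two perfusion results that agree because they are one test. The trial is meant to provide proof of concept and support the Phase 3 dose choice (SAP Section 1), so agreement of that kind should not be read as corroboration.

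**Working it through.** **1. The plan's figure.** A circle of 6 mm diameter has area π × 3² = 28.27, which rounds to the stated 28.3 mm². The denominator is the whole 6 mm circle, the same for every eye and visit.

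**2. Index against area.** Let c be the change in non-perfusion area, b its baseline and k = 28.3. The area model is c = α + βb + τ(treatment) + γ(stratum) + error. Dividing outcome and baseline by k gives c/k = α/k + β(b/k) + (τ/k)(treatment) + (γ/k)(stratum) + error/k. The treatment estimate and its standard error are both divided by k, so t and p do not change. A check on simulated data (70 per arm; the values are arbitrary) agrees:

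| Comparison with vehicle | Area: t, p | Index: t, p |
|---|---|---|
| BID | 0.3186, 0.7504 | 0.3186, 0.7504 |
| QID | -1.4937, 0.1368 | -1.4937, 0.1368 |

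Only the scale differs: the QID estimate is -0.105717 mm² as area and -0.105717 / 28.3 = -0.003736 as Index. With a denominator varying by eye and visit (assumed 85-100% of 28.3 mm²), the Index t values become 0.459 (BID) and -1.286 (QID), so it would then be a distinct endpoint.

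**3. FAZ precision.** Input from the documents: 66 completers per group (SAP 4.13). Inputs assumed, because the documents give no FAZ rates: a share p = 0.5 to 0.8 intact at baseline, and a probability q = 0.05 to 0.20 of switching status, equal in both directions, with no drug effect.

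- Week 24 intact share: p24 = p(1 - q) + (1 - p)q.
- SE of the difference without baseline status: √(2 × p24(1 - p24) / 66).
- SE within baseline strata: √(2 × q(1 - q) / 66).
- Share of the unadjusted variance due to chance baseline imbalance: (1 - 2q)² × p(1 - p) / [p24(1 - p24)].

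| p | q | p24 | SE unadjusted (points) | SE within strata (points) | Ratio | Imbalance share |
|---|---|---|---|---|---|---|
| 0.5 | 0.05 | 0.50 | 8.7 | 3.8 | 0.44 | 81% |
| 0.5 | 0.20 | 0.50 | 8.7 | 7.0 | 0.80 | 36% |
| 0.8 | 0.05 | 0.77 | 7.3 | 3.8 | 0.52 | 73% |
| 0.8 | 0.20 | 0.68 | 8.1 | 7.0 | 0.86 | 26% |

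For example, with p = 0.8 and q = 0.05: √(2 × 0.77 × 0.23 / 66) = 0.073 and √(2 × 0.05 × 0.95 / 66) = 0.038. The unadjusted column ignores any gain from the DRSS strata. If DRSS level predicts FAZ status, the planned analysis does somewhat better than shown.

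**4. FAZ with a drug effect.** Assume 15% of baseline-intact eyes lose an intact FAZ on vehicle and 5% on active, none regain it, 66 per arm, one-sided 5%. At baseline-intact shares of 50 / 70 / 90%:

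- All eyes on Week 24 status: differences 5 / 7 / 9 points, power 14 / 21 / 37%.
- Baseline-intact eyes only (about 33 / 46 / 59 per arm): difference 10 points, power 38 / 48 / 57%.

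The Week 24 contrast is diluted but not zero.

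**The case against.** A reader might infer that these two biomarkers cannot show change at all. The documents do not support that. The Index is expressly a change from baseline and detects change exactly as well as the area does. For the FAZ, an eye disrupted at entry is equally likely to fall in either arm, so the Week 24 difference is unbiased in expectation. Chance imbalance is already inside the unadjusted standard error and does not inflate type I error.

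The plan also covers part of the ground. SAP 4.2 provides in general terms for shift tables of categorical data where appropriate, though it does not name the FAZ. OCTA change in FAZ area gets baseline-adjusted ANCOVA, but OCTA is optional for sites (Protocol 2.16.6), so that coverage is partial.

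It is also tempting to say the FAZ comparison is dominated by chance baseline differences. In the table their share of the variance runs from 81% down to 26%. The statement holds only if FAZ status is fairly stable over 24 weeks, which the documents do not tell us.

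Finally, one might say that ungradable retina is counted as perfused. If 20% true non-perfusion were spread evenly and only 80% of the scan were gradable, a fixed denominator would give 0.20 × 0.80 = 0.16. That is an assumption: OCTA specifications sit in the reading center's acquisition protocol, which is not among the documents. If it did happen, the raw area endpoint would be affected equally.

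What stands after this: baseline FAZ status is available and unused, and the Index test is a duplicate.

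**Conclusion.** The point holds in two limited parts.

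- **FAZ.** The comparison is valid but inefficient, and it cannot distinguish loss from never having been intact. Using baseline status multiplies the standard error by 0.44 to 0.86 under the assumed rates. The gain is large if status is stable and modest if 20% of eyes switch. The ratio does not depend on the number of eyes analyzed.
- **Ischemic Index.** Its duplication of the OCTA non-perfusion-area test is an algebraic identity and needs no assumption beyond both being analyzed on the same eyes. The fault is redundancy. Widefield-FA non-perfusion is a different modality and is not duplicated.

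Both endpoints are exploratory, and the primary analysis, secondary endpoints and sample size are unaffected. This is an inexpensive improvement rather than a necessary correction.

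**What to change.** 1. In SAP 4.10.4, stratify the FAZ comparison by baseline FAZ status (intact or not intact on Visit 1 FA) in addition to DRSS stratum. Name the baseline-to-Week 24 FAZ shift table explicitly, so that loss among eyes intact at entry is visible, and cite the reading center's definition of intact.
2. Drop the separate test of the Ischemic Index, or label it a rescaling of OCTA non-perfusion area. If the reading center already supplies gradable area per visit, use that as the denominator instead. Protocol 3.1.5.1 does not list it among the OCTA gradings, so this needs asking. Nothing in the documents calls for restricting the analysis to eyes imaged on the same device at both visits.

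The cost is SAP wording, settled before database lock as SAP 4.14 requires, and no new imaging. Eyes without a gradable Visit 1 FA drop out of the adjusted FAZ analysis, and their number should be reported by arm. The strata rise from 3 to 3 × 2 = 6. At the 20% cap, the 61B stratum holds about 0.20 × 140 = 28 eyes in each pairwise comparison before the FAZ split, so some cells will be small.

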### 3.2.5 Pharmacokinetic, Pharmacodynamic and Immunogenicity Endpoints

In this study, no pharmacokinetic, pharmacodynamic or immunogenicity data are collected.

## 4 STATISTICAL METHODS

### 4.1 Data Quality Assurance

All tables, figures, and data listings to be included in the report will be independently checked for consistency, integrity, and in accordance with standard Parexel procedures.

### 4.2 General Presentation Considerations

‘Baseline’ is defined as the last available pre-treatment assessment for safety assessments. For DRSS score, the Baseline value is defined as the Screening/Visit 1 result. Pre-treatment values for DRSS were collected at the Screening/Visit 1 using fluorescein angiography in addition to fundus photography whereas Baseline/Visit 2 used fundus photography only. Participants were enrolled into the study and randomized to the study treatment based on the Screening/Visit 1 DRSS result. All other efficacy analyses that do not use DRSS score will use the last available pre-treatment assessment as Baseline. If an assessment is taken on the same day as first administration of study drug, it is eligible to be used as the Baseline value. This is considered acceptable as this measurement is still the best representation of the Baseline value of the given assessment since it is highly unlikely that the study drug could have an impact on any measurement in a short period of time.

‘End of Study’ is defined as the last available post-treatment assessment.

‘Study Day’ will be calculated relative to the date of randomization for untreated randomized participants and relative to the date of first dose for treated participants. If event is prior to the first dose, then study day is calculated as:

$$\text{Date of Event} - \text{Date of Day 1.}$$

If event is after the first dose, then study day is calculated as:

$$\text{Date of Event} - \text{Date of Day 1} + 1.$$

‘Study day 1’ is defined as the date of randomization for untreated randomized participants or the date of first dose for treated participants.

Time to event analyses will be calculated from Study Day 1, including time to DRSS-related endpoints comparing to the Baseline value. These analyses will consider only post-Baseline assessments. The Visit 2/Baseline visit will not be considered.

Duration of Treatment (days) will be calculated as:

$$\text{Last Date of Dose} - \text{First Date of Dose} + 1.$$

Continuous data will be summarized in terms of the mean, standard deviation (SD), median, upper quartile, lower quartile, minimum, maximum and number of observations, unless otherwise stated. The minimum and maximum will be reported to the same number of decimal places as the raw data recorded in the database. The mean, median, lower quartile and upper quartile will be reported to one more decimal place than the raw data recorded in the database. The SD (and SE, if applicable)

will be reported to two more decimal places than the raw data recorded in the database. In general, the maximum number of decimal places reported shall be four for any summary statistic.

Categorical data will be summarized in terms of the number of participants providing data at the relevant time point (n), frequency counts and percentages.

Percentages will be presented to one decimal place except 100%. 100% will be presented as 100% instead of 100.0%. Percentages will not be presented for zero counts. Percentages will be calculated using the number of participants (n) as the denominator. If sample sizes are small, the data displays will show the percentages, but any textual report will describe frequencies only. A missing category shall be included only for categorical variables with missing data. The missing category will be omitted if there were no missing values for that variable.

Changes from baseline in categorical data will be summarized using shift tables where appropriate.

P-values greater than or equal to 0.001, in general, will be presented to three decimal places. P-values less than 0.001 will be presented as “<0.001”. P-values greater than 0.999 will be presented as “>0.999”.

Confidence intervals (CIs) will be presented to one more decimal place than the raw data.

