2.15.1 Schedule of Activities

Table 1 OTT166 201 Phase 2 DR Study: Schedule of Activities (Through Week 24 – Primary Endpoint)

Study Procedure	Screening Visit 1	Baseline (BL) Visit 2	Visit 3	Visit 4	Visit 5	Visit 6	Visit 7	Visit 8 ^a
Week	--	0	4	8	12	16	20	24
Day (visit window)	-21 to -1	1	29 ± 7 days	57 ± 7 days	85 ± 7 days	113 ± 7 days	141 ± 7 days	169 ± 7 days
Screening/Baseline (BL):								
Informed consent	X							
Inclusion/exclusion	X	X						
Medical and ophthalmic history	X							
Demographics	X							
Randomization		X						
Interval Medical Review:								
Review of concomitant medications	X	X	X	X	X	X	X	X
Continue study treatment ^b		X	X	X	X	X	X	
Ocular Assessmentsⁿ:								
Refraction and BCVA (ETDRS)	OU	OU	OU	OU	OU	OU	OU	OU
Slit lamp examination	OU	OU	OU	OU	OU	OU	OU	OU
Assessment of cornea ^c	OU	OU	OU	OU	OU	OU	OU	OU
Intraocular pressure ^d	OU	OU	OU	OU	OU	OU	OU	OU
Indirect ophthalmoscopy	OU	OU	OU	OU	OU	OU	OU	OU
4-wide or 7-field color fundus photography (mandatory) ^e	OU	OU	SE	SE	OU	SE	SE	OU
SD-OCT (widerfield if available)	OU	OU	SE	SE	OU	SE	SE	OU
OCTA (if available)	OU							OU
Wide field Fluorescein Angiography ^m	OU							OU
Gonioscopy	OU							OU

Study Procedure	Screening Visit 1	Baseline (BL) Visit 2	Visit 3	Visit 4	Visit 5	Visit 6	Visit 7	Visit 8 ^a
Week	--	0	4	8	12	16	20	24
Day (visit window)	-21 to -1	1	29 ± 7 days	57 ± 7 days	85 ± 7 days	113 ± 7 days	141 ± 7 days	169 ± 7 days
Non-Ocular Assessments:								
Physical examination ^f	X							
Vital signs ^g	X	X	X	X	X	X	X	X
Adverse events ^h	X	X	X	X	X	X	X	X
IP adherence review ^o			X	X	X	X	X	X
Laboratory Testing:ⁱ								
Hematology, blood chemistry, urinalysis, and HbA1c ^{j,l}	X							X
Pregnancy test, women of childbearing potential ^k	serum	urine	urine	urine	urine	urine	urine	urine

Abbreviations: BCVA: best corrected visual acuity; BL: baseline; ETDRS: Early Treatment Diabetic Retinopathy Study; HbA1c: glycosylated hemoglobin; OCTA: optical coherence tomography – angiography; OU: both eyes; SD-OCT: spectral-domain optical coherence tomography; SE: study eye.

- ^a Participants who are withdrawn from the study before Week 24/Visit 8 will be asked to return to the clinic to complete the end of study assessments.
- ^b Participants will continue to receive study treatment based on exam findings, AE review, and verification that rescue criteria are not met.

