2.16.2 Color Fundus Photography (CFP)

The anatomical state of the retinal vasculature will be evaluated by an ophthalmologist from posterior segment examination and CFP. All digital CFP images need to be taken by a certified technician following an acquisition protocol for modified 7-field stereoscopic color fundus photographs or 4-wide field imaging of the central reading center at the visits indicated in the SoA ([Section 2.15.1](#)).

All CFPs will be transmitted to the central reading center for ETDRS DRSS (see [Appendix 2](#)) grading and storage. The images from the screening visit of both eyes will be used as part of the eligibility assessment regarding the severity of diabetic retinopathy.

CFPs may, in addition, be evaluated for additional, exploratory, endpoints. This may include assessment of microaneurysm turnover ([Nunes 2009](#)) or measurement of diameters of retinal vessels as described previously ([Lundberg 2013](#)). This may involve transmission of CFP to additional central reading centers.

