2.16.4 Fluorescein Angiography (FA)

The anatomical state of the retinal vasculature of the study eye and the fellow eye (only at BL and end of study [EOS]) will be evaluated by FA (widefield preferred). All FAs will be conducted by a qualified technician following an acquisition protocol of the central reading center. The angiographic images will be evaluated by a study ophthalmologist for individual safety decisions. All FA images will be archived electronically at the site as part of the source documentation and sent to the central reading center for evaluation and storage on visits stated in the SoA (Section 2.15.1).

At screening, a standardized set of FA images will be sent to the central reading center for evaluation and eligibility assessment.

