3.1.5 Committees Structure

3.1.5.1 Central Reading Center

The digital retinal images, OCT scans, fluorescence angiographies, and other images as applicable will be assessed by independent central reading centers. Details pertaining to each imaging technique are as follows:

- FP: DRS 4W/7M standard 2-step plus adjudication
- OCT: CI-DME, SRF/IRF, DRIL, TMV (1, 3, and 6mm)
- FA: We will grade ONLY study eye
- OCTA: vessel density, FAZ area, and nonperfusion

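### Does measuring photograph-only DRSS grades at Weeks 4 to 20 against an angiography-assisted Visit 1 baseline call for a Visit 2-referenced analysis?

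*SAP*

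**What the plan says.** SAP section 4.2 defines the DRSS baseline as the Visit 1 result and gives two grounds. The first is imaging: "Pre-treatment values for DRSS were collected at the Screening/Visit 1 using fluorescein angiography in addition to fundus photography", "whereas Baseline/Visit 2 used fundus photography only". The second is design: "Participants were enrolled into the study and randomized to the study treatment based on the Screening/Visit 1 DRSS result". For time-to-event analyses it counts only assessments after baseline and adds: "The Visit 2/Baseline visit will not be considered".

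In the schedules of activities (protocol section 2.15.1, SAP section 6.1), the row "Wide field Fluorescein Angiography" is marked at Visits 1 and 8 only. A footnote adds photographs and FA when progression or CI-DME is diagnosed, before rescue. Color photographs are mandatory at every visit.

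On grading, protocol section 2.16.2 says "All CFPs will be transmitted to the central reading center for ETDRS DRSS" grading. Section 3.1.5.1 lists "FP: DRS 4W/7M standard 2-step plus adjudication". Section 2.16.4 has FA images "sent to the central reading center for evaluation and storage on visits stated in the SoA" without linking them to the DRSS grade.

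SAP section 4.10.2 plans a supplementary analysis of time to improvement of at least 2 steps. It also allows, without a stated trigger, a sensitivity analysis of the responder proportion measured from Visit 2.

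**The concern.** If FA changes the grade, a drop from Visit 1 to a Weeks 4 to 20 visit mixes true improvement with a change of method. Three planned outputs are exposed: the time-to-improvement analysis, the by-visit DRSS summaries in SAP section 4.10.3, and the LOCF sensitivity analysis of the primary endpoint, which can carry a photograph-only grade forward to Week 24.

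If FA raises grades, apparent improvement is inflated in every arm and the contrast is diluted. If Week 24 is also graded from photographs alone, the primary endpoint shares the problem, and the documents do not let a reader rule that out. The one analysis that would match methods is optional, with no stated condition, so on its face it could be run or skipped after results are known. One could therefore ask for a statement of the Week 24 method, a mandatory Visit 2-referenced analysis, a Visit 2-referenced time-to-improvement analysis, and a table of Visit 1 against Visit 2 grades.

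**Working it through.** **1. The plan's own figure.** Inputs from SAP section 4.13: control rate 0.06, difference 0.20 (active 0.26), one-sided alpha 0.05, continuity-corrected chi-square, 90% power. These give 66 per group with power 0.903. Allowing 5% attrition, 66/0.95 = 69.5, rounded up to 70, and 3 × 70 = 210. The figure reproduces and nothing here alters it.

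**2. Which grades are mismatched.**

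| Visit | FA scheduled | Against the Visit 1 baseline |
|---|---|---|
| 1 | yes | is the baseline |
| 2 | no | not used in time-to-event analyses |
| 3 to 7 (Weeks 4 to 20) | no, except before rescue | different method |
| 8 (Week 24) | yes | matched only if FA enters the grade, which is not stated |

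**3. Effect of an assumed shift.** Let q be the share of eyes that photographs alone grade at least 2 steps lower at every photograph-only visit, equal in all arms. No value of q is in the documents. The apparent improvement rate is 1 − (1 − p)(1 − q).

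- Vehicle, q = 5%: 1 − 0.94 × 0.95 = 10.7%.
- Active, q = 5%: 1 − 0.74 × 0.95 = 29.7%.
- Difference: 0.20 × (1 − q) = 19.0 points. With equal true rates it is zero at any q, so the shift creates no false difference.

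**4. Power.** Assumptions: 66 per group, onset spread evenly over six visits, unstratified one-sided log-rank test, no dropout. The last column applies only if Week 24 is graded from photographs alone (exact enumeration of the pooled z test, without continuity correction).

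| q | Log-rank, Visit 1 reference | Primary endpoint, Week 24 photographs only |
|---|---|---|
| 0 | 0.95 | 0.953 |
| 2% | 0.92 | 0.925 |
| 5% | 0.86 | 0.877 |
| 10% | 0.77 | 0.790 |

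On the plan's continuity-corrected scale, the last column reads 0.90, 0.87, 0.81 and 0.72.

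**5. What a Visit 2 reference would buy.** If Week 24 is FA-assisted, a matched analysis must stop at Week 20. Five of six visits then contribute: 26% × 5/6 = 21.7% against 6% × 5/6 = 5.0%, with power about 0.91 at any q. The Visit 1 version has 0.911 at q = 2.5% and 0.902 at q = 3%, so break-even lies between the two. Below it, the matched version is the weaker one. If photographs instead hide improvement in 2 to 10% of eyes, the Visit 1 version keeps 0.95 with Week 24 FA-assisted, and 0.95 to 0.93 otherwise.

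These figures are approximate. Simulated type I error with both arms at 6% ranged from 0.049 to 0.060. Constant power at any q also assumes that shifted eyes can still improve two further steps. By protocol Appendix 2, a level 47 eye read two levels lower is at 35, with only 20 and 10 as separate steps below.

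**6. Would a Visit 1 against Visit 2 table measure the shift?** No. Visit 1 is the selection grade: eyes must read 47, 53 or 61B, and when both qualify the higher-graded eye is chosen (protocol sections 2.8 and 2.13). Regression to the mean then makes Visit 2 look lower with no FA effect. With symmetric grading noise and no shift, one illustration gave 8.6% of eyes at least 2 steps lower against 6.7% higher. Another, with milder eyes commoner, gave 13.2% against 3.3%. The noise is assumed and the size varies with it. Counts such as 5/210 (2.4%, 95% CI 0.8 to 5.5%) therefore do not estimate q. The same selection affects any comparison of Visit 1-referenced with Visit 2-referenced results.

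**The case for a change.** The strongest argument for acting is that the SAP itself cites the imaging difference as a reason for preferring Visit 1, so it can hardly treat the difference as irrelevant at Weeks 4 to 20. One sentence on the Week 24 method would show whether the primary comparison is matched. The photographs for a Visit 2-referenced analysis already exist, and fixing its trigger before unmasking would remove any choice made after seeing results.

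Most of this is factually right. The Week 24 method is not stated, the optional analysis has no trigger, and the supplementary, by-visit and LOCF results do mix methods. What does not follow is a change in analysis. Stating the method leaves the grade and the estimate as they are, and the reading center knows what it used. Turning an optional sensitivity analysis into a mandatory one leaves the primary result untouched. SAP section 4.14 lets blinded review amend analyses with changes final before database lock, and section 4.4.1 provides for a data review meeting before unmasking, so there is a proper occasion to decide.

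The exclusion of Visit 2 from time-to-event analyses is a safeguard. With Visit 1 as baseline, it stops a pre-treatment grade from counting as an event.

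**Conclusion.** No change is called for. The mismatch is documented, but it falls equally on masked, randomized arms, and its size and direction are unknown. For certain it touches only supplementary and descriptive results and any LOCF-carried grades. Visit 1 is sound as the primary baseline on the design ground alone.

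A Visit 2-referenced time-to-improvement analysis would be an extra check on a supplementary analysis. With Week 24 FA-assisted it costs power (0.91 against 0.95 with no shift) unless q exceeds about 2.5 to 3%, and selection on the Visit 1 grade means it could not isolate the effect of FA.

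The open question is whether Week 24 was graded with FA. If it was not, the primary endpoint could lose power (0.953 to 0.877 at an assumed q of 5%) but would not gain a bias toward the drug. This is missing detail that analysts can obtain from the reading center, and in that case running the Visit 2-referenced proportion analysis already allowed in SAP section 4.10.2 is the natural reading of its wording. All power figures rest on the planning rates of 26% and 6% and on assumed values of q, and serve only as illustration.
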